Secondary outcomes include measures of cardiovascular fitness, improvements on neurocognitive testing, everyday activities and quality of life.

Cardiovascular fitness, cognitive performance, activities of daily living and brain activation will be measured at baseline, after 12 weeks of phase 1 and at the end of phase 2.

1. Cardiovascular fitness measure

Cardiovascular fitness will be measured with a modified **Siconolfi Step Test** which has been validated in clinical samples [Marcora *et al.* 2007;Siconolfi *et al.* 1985]. The original test has a step height of 10 inches but we have found that this raises heart rate above 77% of predicted maximum heart rate, making it unsuitable for sub-maximal fitness testing. Our participants will step up and down a 6 inch (152mm) bench for three minutes, completing 17 (step up and down) cycles per minute. Heart rate (HR) will be measured during, immediately after completion of step -test and at one minute intervals for three minutes. The step-test will be paced using a metronome to ensure standard application. This sub-maximal stress test has a very low risk when combined with an exercise safety questionnaire such as the revised **Physical activity readiness questionnaire** (PAR-Q). Waist circumference and BMI (weight (kg) / height² (m)) will also be recorded.

2. Cognitive measures

Participants will complete the following cognitive measures:

- Visual and auditory divided attention task [Dannhauser *et al.* 2005]. This measures speed of processing and attentional set shifting.
- Verbal episodic encoding and recognition task [Dannhauser et al. 2008]
- Halstead Trail Making test (TMT) [Davies 1968]. This measures speed of processing (reaction time) and accuracy (corrected recognition).
- Verbal fluency [Lezack, 1995]
- Working memory tests: digit span forwards/ backwards [Miller, 1956]
- Verbal Reasoning and Working Memory [e.g. Hitch, 1976].

The standard neuropsychological test battery described above will be repeated annually as part of the standard clinical procedure in the memory clinic. This will provide long term follow-up data on all participants until they either make a full recovery or convert to dementia. 3. Measures of quality of life and everyday activities

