Quality of life will be measured on the World Health Organization Quality of Life (WHOQOL) – BREF and change in every day activities on the Alzheimers' Disease Cooperative Study MCI Activities of Daily Living Scale (ADCS-MCI-ADL)[Galasko *et al.* 1997].

4. Measure of brain activation /perfusion with near infrared spectroscopy heamoenephalography (NIRS-HEG)

We will collect brain activation data from all participants at the three time points during administration of the divided attention paradigm which runs for 5 minutes.

We will use a CE marked Oxymon Mk (Artinis, Netherlans) to measure changes in light attenuation at four discrete wavelengths (775,825,,850 and 905 nm) using four laser diodes as light sources and photon multiplier tube as detector. Sensors will be placed over the left prefrontal (F3), the superior parietal (P3) and the occipital cortex (O1) and the right frontal pole (Fp2), according to the international 10-10 system developed for EEG. This portable system does not involve any ionising radiation.

Treatment sessions

1. Physical exercise

Participants will be asked to complete 36 training sessions at a frequency of two to three per week. Half of all the groups (Feedback participants, **FP-group**) will be randomly allocated sound and vibration feedback to help them to stay in a predetermined training zone. Heart rate for the moderate training zone (less than 60% of VO2 max; 65-77% of maximum heart rate) will be determined for each participant from their predicted maximum heart rate (HR max = 220 – age). The other groups will not receive feedback but heart rate will still be measured (Monitoring participants, **MP-group**); this group will receive instruction on utilising subjective reports of effort to guide their optimal level of effort. Assignment to FP-group and MP-group will alternate so equal numbers are obtained for statistical comparison. In addition each participant will be issued

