Feeling very hot and perspiring profusely

Dehydration

Getting lost

Confusion

Wandering

Lack of coordination

Increased recovery time

Cognitive activity related

Headache Fatigue Wrist pain/strain from using mouse

Eye strain

Social activity related

Feelings of frustration Social anxiety

Ethical approval

Ethical approval will be sought for the study from the local research ethics committee.

Statistical analysis

Subjects will serve as their own controls and data will be captured at baseline, following 12 weeks of DSD and at the end of phase two (study week 26). Continuous variables will be compared using paired t-tests and analyses of variance. All statistics will be analysed using SPSS / PC+ version 10.0 (Statistical Package for Social Sciences).

Sample Size.

The planned sample size (n=128) will enable us to detect a change of 0.25 standard deviations in the performance outcomes (details here) with 80% power at the 5% level of significance. The planned comparison between the community based /centre based groups (n=64) will enable us to detect a 0.5SD difference with 80% power at 5% significance. In this feasibility study, it is unlikely that this scale of change will be observed. More important will be our ability to estimate the potential size of the changes. In this case, with 128 subjects we can estimate the change to within +/- 17.5%SD (i.e. the width of the 95% CI will be 35%SD).

Analysis

The principle analysis will focus on the estimation of the change resulting from the intervention. This will be estimated by mean change and 95% CI. Supplementary analyses will employ Repeated Measures ANOVA to examine the changes from Baseline, start of therapy to the end of therapy. These analyses will be extended to assess the role of background covariates, such as age, sex health status etc. Abbott RD, White LR, Ross GW, Masaki KH, Curb JD, Petrovitch H. Walking and dementia in physically capable elderly men. JAMA 2004; 292: 1447-1453.

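### For the repeatedly measured secondary outcomes, the between-group comparisons do not name the pre-programme value as a covariate, although it is collected twice

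*Protocol*

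**What the plan says.** The protocol plans two between-group comparisons.

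- **Centre v community/online.** Under Sample Size: "The planned comparison between the community based /centre based groups (n=64) will enable us to detect a 0.5SD difference with 80% power" at 5% significance. This is the only between-group comparison with a power statement.
- **Feedback (FP) v monitoring (MP).** Under Treatment sessions, Physical exercise: "Assignment to FP-group and MP-group will alternate so equal numbers are obtained for statistical comparison". The same paragraph also calls the allocation of feedback random and applies it to half of the groups. No power is given.

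On method, Statistical analysis says "Continuous variables will be compared using paired t-tests and analyses of variance". The Analysis paragraph makes mean change with a 95% CI the principal estimate and repeated-measures ANOVA over the three time points supplementary. It then adds: "These analyses will be extended to assess the role of background covariates, such as age, sex health status etc". The pre-programme value of the outcome is not in that list.

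On data, Outcome measures says that fitness, cognitive performance, daily activities and brain activation "will be measured at baseline, after 12 weeks of phase 1 and at the end of phase 2". Times 1 and 2 therefore both precede the phase two programme, and Time 3 follows it. The main outcome (compliance, feedback on the interventions, continued engagement) has no pre-programme value.

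**The concern.** When an outcome has been measured before the programme, a group comparison that adjusts for that value is more precise than one that ignores it. With equal variances at the two times, it is also more precise than one that subtracts it. The protocol names methods and covariates in some detail and powers one comparison on the unadjusted basis, but does not put the earlier value to this use.

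At stake is the width of the intervals for the FP v MP and centre v online differences. A by-product is also lost: the Time 2 to Time 3 correlation. One study aim is to size a later randomised trial, and that correlation is what a sample size based on ANCOVA would need.

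**Working it through.** **Inputs from the protocol.** N = 128; 64 per group (128/2; only 64 in each group reproduces the stated power); difference 0.5 SD; power 80%; 5% significance (sidedness not stated).

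**Assumed.** Correlation ρ between pre- and post-programme values, range 0.3 to 0.7, because the protocol gives none. Equal variances at each time and independent participants.

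**1. Reproduce the stated figures.**
- Two-sided two-sample t-test, 64 per group, 0.5 SD: power 80.1%; 63.8 per group needed for 80%. One-sided would give 87.9%, and 64 in total (32 per group) would give 50.4%. So the figure is two-sided with 64 per group, and no covariate or correlation enters it.
- Within-person: 128 pairs at 0.25 SD give 80.2%. The 95% half-width is 1.96/√128 = 0.173 SD (0.175 with the t quantile), which matches the stated 17.5% and is in units of the SD of change.

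**2. Variance of the group difference, relative to an unadjusted Time 3 comparison.**
- ANCOVA on one earlier value: 1 − ρ²
- Change score: 2(1 − ρ)
- Ratio of ANCOVA to change score: (1 − ρ²) / [2(1 − ρ)] = (1 + ρ)/2

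For any ρ strictly between 0 and 1, both 1 − ρ² and (1 + ρ)/2 are below 1. ANCOVA is then more precise than either alternative.

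**3. Power with 64 per group.** The t-test is run at effect size 0.5/√(relative variance). For example, at ρ = 0.5 ANCOVA has variance 0.75, and 0.5/√0.75 = 0.577.

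If the 0.5 SD is in units of the outcome SD:

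| ρ | Unadjusted Time 3 | Change score | ANCOVA, one value |
|---|---|---|---|
| 0.3 | 80.1% | 66.0% | 83.7% |
| 0.5 | 80.1% | 80.1% | 90.0% |
| 0.7 | 80.1% | 95.2% | 97.6% |

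If the 0.5 SD is in units of the SD of change, the relative variance is (1 + ρ)/2:

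| ρ | Change score | ANCOVA, one value |
|---|---|---|
| 0.3 | 80.1% | 93.6% |
| 0.5 | 80.1% | 90.0% |
| 0.7 | 80.1% | 86.1% |

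The two readings move in opposite directions as ρ rises, so the protocol needs to say which SD is meant.

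**4. Interval width.** In outcome-SD units the unadjusted half-width is 1.98 × √(2/64) = 0.350. With ANCOVA at ρ = 0.5 it is 0.350 × √0.75 = 0.303.

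**5. Grouped delivery.** Centre participants meet in groups of 8 (Socialising section). With an assumed intraclass correlation of 0.05, the design effect is 1 + 7 × 0.05 = 1.35. The unadjusted 80% falls to about 68% if all participants are in such groups. The powers above are therefore comparisons between methods and should not be read as achievable levels.

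**The case against.** The power sentence is correct as written. Covariates for secondary comparisons are often left to the SAP, and the covariate list is open-ended. That limits the point to an improvement of stated choices. It does not remove it: the protocol itself names the tests, the covariates and the power basis, and a few more words there would settle the model.

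Several stronger readings are tempting, and the protocol does not support them.

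- **That every outcome could be adjusted.** The main outcome has no earlier value.
- **That the plan discards the pre-programme data.** Mean change and repeated-measures ANOVA both use it, and no test is assigned specifically to the between-group contrasts. The change score is therefore a fair comparator, and against it the gain at ρ = 0.7 is only 2.4 points (95.2% to 97.6%) on the outcome-SD reading.
- **That both comparisons are powered at 80%.** Only centre/community has a power statement.
- **That change scores are simply inferior.** Centre v online is not said to be randomised. Without randomisation, ANCOVA and change scores can estimate different effects, and neither is automatically right.
- **That the main precision statement is affected.** The emphasis on estimation, with its ±17.5% SD, concerns within-person change in all 128 participants. A between-group ANCOVA leaves that interval as it is.

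**Conclusion.** The point stands in a limited form. For fitness, cognition, daily activities and brain activation, the protocol does not name the pre-programme value as a covariate in the between-group comparisons, although it is collected at Time 1 and Time 2. Adjusting for it would improve precision at any correlation strictly between 0 and 1, given equal variances.

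The size cannot be fixed from the protocol. Over ρ = 0.3 to 0.7, power rises from 80% unadjusted to about 84–98% on the outcome-SD reading, or from 80% for a change score to about 94–86% on the SD-of-change reading. All these figures assume independent participants, which delivery in groups makes optimistic.

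The case is cleanest for FP v MP, where the study controls allocation (described both as random and as alternating). For centre v online the model is worth pre-specifying, but a reader should not infer that adjustment removes selection. Nothing here makes the stated 80% wrong.

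**What to change.** In the Analysis paragraph:

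1. State that the FP v MP difference at Time 3, for each repeatedly measured secondary outcome, will be estimated by ANCOVA with the Time 2 value of the same measure as covariate (optionally Time 1 as well). Report it with a 95% CI and the observed Time 2 to Time 3 correlation, using an analysis that allows for allocation and delivery in groups.
2. For centre v online, pre-specify the same model, but present it as an adjusted, non-randomised comparison alongside the change-score result.

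In the Sample Size paragraph:

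3. Label the 0.5 SD / 80% figure as unadjusted and as applying to centre/community only, and say whether SD means that of the outcome or of its change.

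The cost is a few sentences and no new data. The analysis loses one degree of freedom per covariate and needs a rule for participants without a Time 2 value, for example use of the Time 1 value or a mixed model.

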of activity as well as performance. The Lumosity program provides feedback on performance and participants can do additional activities if they choose.

3. Socialising

Socialising will take place in groups of 8 for the centre based participants. Participants will attend for 12 weeks, a 2.5 hour long session at facilities provided by ACL Essex. All sessions will broadly follow the same format.

0-15 Minutes: Greeting and light chair based balance and stretching activities. These activities will be lead by a video prompt (video: Active Health 50+ from *Age Concern*) and monitored by research staff.

15-45 Minutes: Reporting on and presentation of completed tasks from previous week and advice on practicalities of tasks.

45 - 60 Minutes: Break

60 to 120 Minutes: Group based creative or physical activity.

120 to 150 Minutes: Feedback and relaxation training (video guided relaxation)

The first two group sessions will be used to introduce participants to each other and familiarise them with computers and using a mouse to facilitate the cognitive training sessions. The sessions will be lead by trained tutors and detailed instructions on the scope and sequencing of activities will be provided in a training manual. Creative and physical activities included are designed to stimulate cognition and emphasis is placed on variety and multi-sensory stimulation. Home activities described in detail in Appendix D. Group based activities described in detail in Appendix E.

Motivating adherence.

Participants will be made aware that specific persuasion techniques will be implemented to improve their long term commitment to physical activity, cognitive stimulation and socialising. These will include the principals of reciprocity, authority, scarcity, liking and social proof.

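### The 80% power for community v centre assumes 128 independent participants, although at least the centre arm is treated in groups of 8

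*Protocol*

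**What the plan says.** The Sample Size paragraph gives two power statements and one precision statement.

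- Whole sample: "The planned sample size (n=128) will enable us to detect a change of 0.25 standard deviations" with 80% power at the 5% level.
- Between groups: the comparison of community based and centre based "groups (n=64) will enable us to detect a 0.5SD difference with 80% power at 5% significance".
- Precision: with 128 subjects, "we can estimate the change to within +/- 17.5%SD".

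It mentions no grouping, ICC or design effect. The Statistical analysis section names paired t-tests and analyses of variance, with repeated measures ANOVA as a supplement. It names no group term.

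Delivery is described elsewhere. Under Treatment sessions, Socialising: "Socialising will take place in groups of 8 for the centre based participants", in 2.5-hour tutor-led sessions over 12 weeks. Cognitive training is partly individual and partly in groups of unstated size. Under Physical exercise, half of all the groups "will be randomly allocated sound and vibration feedback to help them to stay in a predetermined training zone". The rest are monitored without feedback, and assignment alternates. The protocol does not say how participants come to be centre based or online, and it gives no group size for online participants. I take the community based arm of the power sentence to be the online group, since no other counterpart to the centre arm is described.

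**The concern.** People who spend 12 weeks in the same small group, with the same tutor, tend to end up more alike than people drawn from different groups. This protocol intends that. The introduction on social exercise credits group cohesion with better compliance, and the section on motivating adherence uses social proof and encouragement in the group setting as tools. Assuming no within-group correlation sits badly with that rationale.

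The centre groups lie wholly inside one arm of the comparison, so correlation within them adds variance to the difference between arms. Three things follow: the stated power is too high, an analysis of individuals that ignores group gives a standard error that is too small, and confidence intervals are too narrow.

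The last point matters most here. The protocol prefers estimation to testing, and one of its aims is to size a future randomised trial. Standard errors that are too small, and no ICC, would be carried into that trial.

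**Working it through.** **Inputs.** From the Sample Size paragraph: 0.5 SD, 5% (sidedness not stated), n = 64, read as per group. From Socialising: groups of 8, so 64/8 = 8 centre groups. **Assumed:** ICC 0.02, 0.05, 0.10, because the protocol gives none.

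**1. Reproduce the stated figures.**
SE = √(1/64 + 1/64) = 0.1768, and 0.5/0.1768 = 2.83. Two-sided power is 80.1% (noncentral t, 126 df) or 80.7% (normal). One-sided gives 88.2%, and 32 v 32 gives about 50%. The stated 80% is therefore two-sided, 64 per group, independent participants.
CI half-width: t(127) × 1/√128 = 1.979 × 0.0884 = 0.175 SD, as stated.

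**2. Allow for groups of 8.**
Design effect DE = 1 + (8 − 1) × ICC = 1.14, 1.35, 1.70.
- Centre arm only: SE = √(DE/64 + 1/64).
- Both arms (assumed structure): SE = √(2 × DE/64).

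Power is computed in two ways. The normal approximation shows the design effect alone. Noncentral t with group-level degrees of freedom also counts the cost of having few groups. For the centre arm only, the Satterthwaite df = (DE + 1)² / (DE²/7 + 1/63). At ICC 0.05 this is 5.52/(0.260 + 0.016) = 20.0. For both arms, df = 16 − 2 = 14.

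| ICC | Centre only, normal | Centre only, group df | Both arms, normal | Both arms, group df |
|---|---|---|---|---|
| 0 | 80.7% | 77.6% | 80.7% | 74.9% |
| 0.02 | 78.1% | 74.5% | 75.5% | 69.3% |
| 0.05 | 74.2% | 69.9% | 68.2% | 62.0% |
| 0.10 | 68.2% | 63.1% | 58.3% | 52.4% |

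The first row matters: part of the loss in the group-df columns is there at ICC 0 and comes from the degrees of freedom, not from correlation.

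**3. Detectable difference at ICC 0.05, 80% power.**
- Centre only: (1.96 + 0.8416) × √(2.35/64) = 2.80 × 0.1916 = 0.537 SD; with group df, 0.564 SD.
- Both arms: 2.80 × √(2.70/64) = 2.80 × 0.2054 = 0.575 SD; with group df, 0.619 SD.

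**4. Type I error of a test that ignores grouping, ICC 0.05.**
The true SE exceeds the assumed SE by √(2.35/2) = 1.084 (centre only) or √1.35 = 1.162 (both). The real critical value is then 1.96/1.084 = 1.81 or 1.96/1.162 = 1.69, so the two-sided error is about 7% or 9%.

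**5. Whole-sample CI half-width, ICC 0.05.**
- Centre only: 1.96 × √(2.35/64)/2 = 1.96 × 0.0958 = 0.19 SD; with 20 df, 0.20 SD.
- Both arms: 1.96 × √(1.35/128) = 1.96 × 0.1027 = 0.20 SD; with 15 df, 2.131 × 0.1027 = 0.22 SD.

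The range is 0.19 to 0.22 SD against the stated 0.175. It applies to change measured after the group sessions.

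**6. Feedback v monitoring.** No power is stated, so there is no figure to correct. The Physical exercise section assigns this factor to whole groups. The group is then the unit of allocation, and an ANOVA on individuals understates the SE at any ICC above zero.

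**The case against.** **The size rests on an assumed ICC.** True. Much of the treatment is individual: exercise with home visits, weekly telephone calls and part of the cognitive training. The ICC could be small. At 0.01 with only the centre arm grouped, power is 79% on the design effect alone. The direction does not depend on the assumption, but whether the shortfall is material does.

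**The comparison is secondary.** The main outcome is development and implementation of the programme, and the principal analysis is within-person mean change with a 95% CI. The protocol itself doubts that a change of the stated scale will be seen, and ranks estimation higher. This stands, and it limits the severity. It does not remove the point, because grouping widens the interval too.

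**A random effect is an analysis-plan detail.** Fair for the model, and the ANOVA named does not exclude a group factor. The excess type I error is therefore conditional on an individual-level analysis. The power figure, however, is stated in the protocol and needs independence.

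**Stronger readings that the protocol does not support.** A reader might infer that participants are allocated to centre or community in groups of 8, giving 8 v 8 groups. Allocation by whole groups is described only for feedback v monitoring, and groups of 8 only for centre participants. The both-arms columns are thus an assumed upper scenario. A reader might also expect that adjusting for the Time 2 value would restore 0.50 SD. That needs a correlation the protocol does not give, and it depends on which SD is meant. With an assumed correlation of 0.6, adjustment multiplies the SD of a single score by √(1 − 0.36) = 0.80, but the SD of a change score only by √(0.64/0.80) = 0.894. In the both-arms case 0.619 then becomes about 0.55.

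**Conclusion.** The point holds in limited form. The 80% requires 64 v 64 independent participants, and the protocol's own delivery plan makes independence implausible in at least the centre arm.

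With only that arm grouped, the reading the text supports directly, power over ICC 0.02 to 0.10 runs from about 78% down to 68% on the design effect alone, or 75% down to 63% with group-level degrees of freedom. If online participants also met in eights, power at ICC 0.05 would be about 62% to 68%.

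All of these sizes rest on the assumed ICC range and on equal groups of 8. Feedback v monitoring raises a separate and more direct problem, since whole groups are assigned. Severity is moderate: this is a secondary comparison in a feasibility study, and the wording can be put right without altering the design.

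**What to change.** 1. In the Sample Size paragraph, say that 80% assumes independence. Give an ICC range with the resulting power, detectable difference and CI width, or present community v centre as estimation only.
2. State whether online participants meet in fixed groups, and of what size.
3. Analyse community v centre and feedback v monitoring with a mixed model that has a random group effect, confined to the centre arm if online participants are not grouped. Adjusting for the Time 2 value is a sensible addition, but it should not be used to defend the 0.5 SD figure.
4. Report the estimated ICC with its interval, for use in sizing the future trial.

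The cost is wording and a line of model code. No extra patients or assessments are needed, provided that group membership is recorded. The stated power becomes somewhat less favourable.
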